Among biological risk factors, apolipoprotein epsilon-4 (APOε4) allelic status^{8,12} and positron emission tomography (PET) based amyloid burden^{5,7,13-15} have received the most attention in the risk disclosure literature, albeit in cognitively healthy individuals primarily. These studies indicate that patients' desire for risk information is high but varies as a function of how much they know about DAT and AD biomarkers¹⁶⁻¹⁸. There exists great variability in reasons for requesting risk disclosure, ranging from basic curiosity to family planning^{6-7,16-17}. Additionally, post-disclosure, even cognitively healthy participants have difficulty understanding feedback language (e.g., interpreting a "positive" biomarker as a "good" outcome¹²). Comparing across these single-source risk disclosure studies may be misleading, however, as none have directly compared what type of feedback patients would want to receive given a menu of all possible risk factors. In the absence of such a study, we suggest that clinical, genetic, and biomarker feedback is likely to be processed differently by patients. Genotype and family history are static, representing non-modifiable susceptibility. Cognitive test scores represent concrete measurements of changes that may already be apparent to patients and caregivers. In contrast, biomarkers are unfamiliar measurements of the individual's underlying level of AD pathology and are probabilistic rather than deterministic for a diagnosis of DAT. In light of these differences, the need to compare patient preferences for different sources of risk feedback is critical.

Advancement 1: This study will conduct a needs assessment of diverse patients' and informants' risk disclosure preferences. Aim 1 will evaluate patient and informant preferences for different sources of information used to determine DAT risk (see Table 1). Our inclusion of both patients and informants is especially relevant given our¹⁹ and others'²⁰⁻²² work showing discrepancies in self- and informant-rated cognitive deficits. The proposed project will include a sample that is racially diverse (see Advancement 2), unlike prior studies that have focused primarily on White older adults. Furthermore, the sample will include both cognitively symptomatic (MCI) and intact older adults, rather than focusing on healthy populations alone. Results will describe the unique disclosure needs of African-American and White participants and their families.

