1.1 Do African-American and White participants or co-participants differ in their interest in receiving certain types of DAT risk information? The study will evaluate group differences in participant and co-participant interest in and actual preference for feedback at five levels: (1) no information about AD risk, or risk information based on (2) standard clinical measures, (3) genetic information, (4) quantitative structural neuroimaging, (5) amyloid and tau PET. Exploratory analyses will assess whether group differences also exist based on clinical research diagnosis (normal vs. MCI), and whether participants and their co-participants agree.

1.2 Do African-American and White participants or co-participants differ in their perspectives on/rationale for certain types of DAT risk feedback? This study will assess whether African-American and White participants and co-participants identify different primary reasons for risk disclosure (i.e., basic curiosity, emotional reason, financial planning, medical planning, legal planning, social/family planning, or other). Exploratory analyses will assess whether group differences also exist based on clinical research diagnosis (normal vs. MCI), and whether participants and their co-participants agree.

1.3 Which characteristics predict risk disclosure interest in African-American vs. White participants and co-participants? This study will evaluate whether African-American and White participants and co-participants differ in their perceived threat of DAT, perceived benefits of risk disclosure, and perceived barriers to using risk information. We will also determine whether different factors (including personal demographic characteristics and the aforementioned perceived threat, benefits, and barriers) predict risk disclosure interest in different groups. Exploratory analyses will assess whether group differences also exist based on clinical research diagnosis (normal vs. MCI), and whether participants and their co-participants agree.

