1.4 Which components of feedback do African-American and White participants or co-participants see as most important? This study will evaluate whether African-American and White participants and co-participants differ in their perspectives on the relative importance of different component of risk disclosure (e.g., educational materials, visual aids, follow-up coordination with providers). Exploratory analyses will assess whether group differences also exist based on clinical research diagnosis (normal vs. MCI), and whether participants and their co-participants agree.

Objective 2: to develop person-centered, culturally-informed protocols for disclosure of different combinations of Alzheimer's dementia risk factors. Building on the results of Objective 1, we will produce protocols for communication of DAT risk, with attention to specific adaptations in style or content based on the above noted individual factors. In particular, protocols will specify (a) effective methods of communicating risk conferred by each data source, (b) information designed for patients versus informants, (c) psychoeducation needs, and (d) resource/support needs. Through piloting in Stage II, we will evaluate three outcomes in both participants (those receiving the feedback) and co-participants:

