3.4.2.1 Stage I

Primary Outcome 1.1 (Differences in risk disclosure interest and preferences): To analyze the dichotomous yes/no interest outcomes, chi-squared analyses will be used to compare the proportion of African-American and White participants who endorse interest in receiving feedback at each level, for caregivers and patients separately. Given that there are five levels of risk disclosure feedback, five comparisons will be conducted; to account for the relatively small sample size, a conservative Bonferroni correction for multiple comparisons will be implemented ($\alpha = .05/5 = .01$). To analyze the Likert-style interest outcomes, either independent samples *t*-tests or Mann Whitney U tests will be used to compare mean interest level in African-American and White participants for each of the five risk disclosure levels, again using a Bonferroni correction. Further exploratory correlation analyses will determine agreement between caregiver and informant interest in African-American and White subgroups, separately.

Primary Outcome 1.2 (Differences in risk disclosure rationale): This study will assess whether African-American and White participants and co-participants identify different primary reasons for risk disclosure (i.e., basic curiosity, emotional reason, financial planning, medical planning, legal planning, social/family planning, or other), a Fisher's Exact test will be used, comparing frequency of reason endorsement. These analyses will be conducted for patients and informants separately; however, we will also explore agreement among dyad members.

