Primary Outcome 1.3 (Patient characteristics that influence preferences): We will utilize a regression approach to determining patient characteristics and perspectives that shape level of interest. More specifically, we will create mixed linear models to quantify the fixed effects of four sets of variables (participant factors [demographics, baseline anxiety and depression, DAT knowledge], ADI Perceived threat of DAT, ADI Perceived benefits of this level of risk disclosure, ADI Perceived barriers to using this risk information), as well as the random effects attributable to the dyadic relationship. This approach will allow us to calculate the intra-class correlations representative of the effect of the dyadic relationship. Furthermore, given the likely effect of dyadic role ('patient' or informant) on perceived threat, perceived benefits, and perceived barriers, the interaction terms (e.g., role by threat, role by benefits, role by barriers) will also be included in the model. It is expected that the effect of the dyadic relationship will be significant; therefore, additional subgroup analyses examining predictors of risk disclosure interest in caregivers and patients *separately* will be conducted.

Primary Outcome 1.4 (Differences in importance of risk disclosure components): To analyze the Likert-style importance outcomes, either independent samples *t*-tests or Mann Whitney U tests will be used to compare mean interest level in African-American and White participants for each of the feedback components, again using a Bonferroni correction. Further exploratory correlation analyses will determine agreement between caregiver and informant interest in African-American and White subgroups, separately.

Secondary Outcome (Qualitative Information from Semi-Structured Interviews): In combination with the semi-structured interviews, we will therefore record and transcribe the narrative responses of patients and caregivers. After basic 'cleaning' of the data (removal of articles, non-content utterances, and additional identified 'stop' words), the text will be analyzed using R Statistical Software for most commonly used words or phrases by race. A Topic Modeling approach (akin to an exploratory factor analysis for text analysis) will be utilized to identify central themes (the 'factors') and associated terms or phrases (the 'items') by race.

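### For Outcomes 1.1 and 1.4, dyad agreement is to be judged by correlation, which does not respond to a constant difference between the two roles

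*Combined protocol and SAP*

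**What the plan says.** Section 2.2 poses an exploratory question under each of 1.1 to 1.4: "whether participants and their co-participants agree". For the interest ratings (Outcome 1.1) and the importance ratings (Outcome 1.4), Section 3.4.2.1 answers it with one repeated sentence: "Further exploratory correlation analyses will determine agreement between caregiver and informant interest in African-American and White subgroups, separately". It gives no coefficient, no paired comparison of the two roles and no match rate.

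The main tests around that sentence compare races. The yes/no choices are tested "for caregivers and patients separately", and the 1-5 ratings by t-test or Mann-Whitney. Under Section 3.3.1 both members of the dyad complete the interest ratings, the yes/no checklist and the importance ratings.

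Two wording slips sit in the same text:
- Caregiver and informant are each set against patient elsewhere in the section ("for caregivers and patients separately"; for 1.2, "conducted for patients and informants separately"), so both words denote the co-participant.
- Outcome 1.4 concerns importance, but its test is described as one to "compare mean interest level in African-American and White participants for each of the feedback components", and the agreement sentence again says interest.

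**The concern.** Agreement asks whether the two members of a dyad give the same answer. Correlation asks whether dyads in which one member rates high are also those in which the other rates high. If co-participants as a group want about one point more information than participants, the correlation can be high while few dyads match, and the planned sentence would let that be reported as agreement.

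The difference between roles has a use in this project. Objective 2 says the protocols will specify "information designed for patients versus informants", so which role rates higher, and by how much, is worth knowing. Section 2.1 justifies recruiting both roles by earlier work on "discrepancies in self- and informant-rated cognitive deficits". That concerns rated deficits, not interest or importance, so it is context and not evidence that a shift will occur here.

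**Working it through.** **Inputs from the plan.** 25 dyads per race (Section 3.1.1, within a total of up to 60); interest and importance both rated 1 to 5 (Section 3.3.1). The plan gives no expected value or sample-size figure for agreement, so there is no stated figure to reproduce. The ratings below are assumed, for illustration only.

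**Step 1. Algebra.** Add a constant c to every co-participant rating Y.
- Pearson r = cov(X,Y)/(s_X s_Y): the covariance and s_Y do not change, so r does not.
- Spearman and Kendall use only the order within each role, which does not change.
- Consistency ICC for two raters = (MSR − MSE)/(MSR + MSE), with MSR the between-dyad and MSE the residual mean square. The shift enters only the between-role mean square MSC, which is absent.
- Absolute-agreement ICC = (MSR − MSE)/(MSR + MSE + 2(MSC − MSE)/n). MSC is present, so this one falls.

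**Step 2. Fixed example, 25 dyads.** Participant ratings are 1, 2, 3, 4 in 6, 6, 7, 6 dyads, in ascending order. The co-participant rating is the participant's plus (0, 0, 0, +1, −1) repeated five times, limited to 1-4, and then +0 or +1. Before the shift, 17 dyads match, 4 differ by +1 and 4 by −1. The SD of the differences is √(8/24) = 0.577, and the 95% half-width is 2.064 × 0.577/5 = 0.24. After the shift only the 4 dyads at −1 match.

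| | No shift | Co-participant +1 |
|---|---|---|
| Pearson | 0.87 | 0.87 |
| Spearman | 0.87 | 0.87 |
| Kendall | 0.795 | 0.795 |
| Consistency ICC | 0.87 | 0.87 |
| Absolute-agreement ICC | 0.87 | 0.62 |
| Identical ratings | 17/25 = 68% | 4/25 = 16% |
| Mean participant minus co-participant (95% CI) | 0.00 (−0.24 to 0.24) | −1.00 (−1.24 to −0.76) |

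**Step 3. Ratings capped at 5.** Simulation of 4,000 sets of 25 dyads: bivariate normal with SD 1, rounded and limited to 1-5, co-participant centre shifted by 0 or 1. Averages over sets, no shift → shift of 1:

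| Centre, latent correlation | Pearson r | Identical | Size of mean paired difference |
|---|---|---|---|
| 3.5, 0.8 | 0.72 → 0.68 | 55% → 31% | 0.00 → 0.84 |
| 4.2, 0.8 | 0.70 → 0.60 | 61% → 47% | 0.00 → 0.62 |
| 3.5, 0.5 | 0.45 → 0.41 | 39% → 30% | 0.00 → 0.83 |

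The invariance is no longer exact, and the contrast shrinks near the ceiling. In each row r still changes by 0.10 or less, while the paired difference shows most of the shift.

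**Step 4. What other summaries could recover.** With both SDs and a Pearson r on complete pairs, var(d) = s₁² + s₂² − 2 r s₁ s₂. In Step 2 each variance is 1.26, so var(d) = 1.26 + 1.26 − 2 × 0.8677 × 1.26 = 0.333, and the SD is 0.577 as found directly. The paired CI is therefore derivable. The match rate is not. Take the same participant ratings and let the co-participant copy them, except that one 1 and one 3 are exchanged. Means and SDs are as in the unshifted example. The squared differences again sum to 8, so r = 1 − 8/(2 × 24 × 1.26) = 0.87 again. Yet 23/25 = 92% match instead of 68%.

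**Step 5. Yes/no checklist.** A constant shift is not the issue here. If the sentence covers the checklist, a phi coefficient with the two role proportions fixes all four cells and so the match rate. If it does not, only the proportions remain. With 20 of 25 saying yes in each role, the fewest both-yes dyads is 2 × 20 − 25 = 15, so the match rate lies anywhere from 15/25 = 60% to 100%.

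**Step 6. No single coefficient is enough.** With 21 dyads at (5,5), 2 at (4,5) and 2 at (5,4), r and the absolute-agreement ICC are both −0.09, although 84% match and the mean difference is 0.00 (±0.17).

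**The case against.** The strongest reply is that the plan would expose a shift anyway. Question 1.1 asks "Do African-American and White participants or co-participants differ in their interest", and question 1.4 likewise names both roles, so role-specific means by race are the natural output and would stand beside the correlation. The word participants in the rating analyses need not exclude co-participants, since the yes/no sentence uses it for both roles. The Outcome 1.3 model has a dyad ICC and role interactions. It would normally carry a role main effect for interest, and question 1.3 in Section 2.2 does ask about race. The word correlation also does not rule out an absolute-agreement ICC.

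Most of this stands. A reader might infer that a role difference would go unseen, or that no paired interval could be obtained; the documents do not support either. What remains is that none of these outputs is assigned to the agreement question. The 1.3 model covers neither importance ratings nor the checklist. An absolute-agreement ICC alone gives neither the direction nor the size of a difference. The match rate on the 1-5 ratings cannot be rebuilt from means, SDs and r.

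It is also fair to say that the fixed example is built so that the shift never meets the top of the scale; Step 3 gives the more realistic, smaller contrast. And a reader might infer from the sentence that co-participants are to be correlated with themselves. Section 2.2 names the intended pair, so that is a clerical slip, as is interest for importance.

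**Conclusion.** The point holds as a minor one about method. Correlation is named as the means of determining agreement, and the usual coefficients cannot do that when the roles differ in level. In the assumed examples a 1-point shift leaves r unchanged (0.87) or lowers it by 0.04 to 0.10, while exact agreement falls from 68% to 16%, or by 9 to 24 percentage points with capping. These figures illustrate the property; they do not forecast this trial, whose rating distributions and role difference are unknown.

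The consequence is limited. The agreement question is labelled exploratory and the primary race comparisons do not use it. A reader might infer that a misleading coefficient would determine what Stage II gives to each role, but no section ties Stage II content to a coefficient.

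**What to change.** In Section 3.4.2.1, Outcomes 1.1 and 1.4:
- For the 1-5 interest and importance ratings, report any correlation as association only. Beside it give the mean participant-minus-co-participant difference with 95% CI and the percentage of dyads with identical ratings, by race and labelled exploratory. An absolute-agreement ICC or weighted kappa may be added, but should not be read alone when ratings cluster at the ceiling.
- For the yes/no checklist, report percent agreement and the paired difference in proportions.
- While editing, name the pair as participant versus co-participant in both places, and write importance for interest in 1.4.

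Cost: SAP wording and a little more descriptive output from the same paired data. Sample size, data collection and the primary tests are unchanged.

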Phone Conferencing Sessions: Participants/co-participants who are interested in engaging in a virtual visit but do not have access to the required technology or otherwise feel uncomfortable with a video visit will be offered the opportunity to complete the session via phone.

Informed Consent for Virtual Visits: The informed consent document will be emailed to participants and co-participants at the time of scheduling, to provide the recipient enough time to review the document. Prior to other study activities, a study team member will set up a phone call to review the consent paperwork together. At this phone appointment, a study team member will explain each section of the informed consent document, pausing to answer questions or clarify misunderstandings. In parallel with the procedures used in in-person sessions, the study team member will also use the Decision-Making Capacity Tool to ensure that the individual providing consent is able to fully understand the decision he/she is making prior to providing consent. After the informed consent document has been reviewed, eligible participants/co-participants will be asked to provide electronic signature on this form. This can be completed through two methods: (a) the patient can download, sign, scan, and email the form back to the study team member, who will additionally sign as witness and study representative, or (b) the SignNow platform will be used to provide electronic consent. SignNow is a secure platform offered through University of Michigan, which is HIPAA-compliant and approved by Health Information Technology Services (HITS). A copy of the form, with all signatures, will be emailed to the participant/co-participant.

Co-Participant Screening for Virtual Visits: As noted above, all co-participants must be cognitively intact based on screening or recent evaluation. In lieu of in-person screening, co-participants will be asked to complete a brief phone or video screen (the Blind version of the Montreal Cognitive Assessment [MoCA]) after informed consent, but prior to other study activities. As with in-person visits, co-participants whose scores fall below the cutoff for impairment will be considered ineligible for study participation. Their respective participants will also be asked to delay scheduling of their virtual visit until they can identify another interested and eligible co-participant.

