Ineligible participants or co-participants will be excluded, but paid for their time. Eligible participants and co-participants will be included in the research study, and will continue the session to complete questionnaires and a semi-structured interview. The semi-structured interview will be recorded, as the qualitative responses from participants/co-participants will be analyzed as secondary outcomes in the study. In-person sessions are recorded using a secure, HIPAA-compliant voice recorder, with all sessions transferred to a secure drive, password protected, and deleted from these recorders immediately after the session. Virtual visit interviews will be recorded using BlueJeans, Zoom for Health, or using the voice recorder with the phone call on speakerphone; similarly, these audio files will be de-identified, transferred to a secure drive, and password protected. Participants and co-participants will also complete a Beck Anxiety Inventory and Geriatric Depression Scale – 15 Item after these procedures, in order to monitor anxiety and mood (see Section 3.5.1 Monitoring). All in-person sessions will take place in the PI's (ARF) laboratory at the University of Michigan. All virtual sessions will be completed by study team members either at the [name] laboratory, or in a secure, private location. Individuals will receive \$20 compensation for their participation in the study, paid via check after the session.

Conceptual Model. The conceptual model for understanding feedback preferences is adapted from the Health Belief Model³⁰, (Figure 1). The resulting model contains three domains: 1) Perceived Threat of AD (i.e., perceived vulnerability to and seriousness of an AD diagnosis); 2) Feedback Expectancies

(i.e., rationale for learning about risk, perceived barriers to learning about or dealing with risk information); and 3) Feedback Preferences (i.e., the type of risk disclosure desired).

Primary Outcomes:

Questionnaires: In addition to the qualitative information gathered during the semi-structured interviews (see below), several formal questionnaires will be administered to provide quantitative information:

[figure not shown]

Figure 2. Conceptual Model for Risk Disclosure Preferences

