3.4.2.2 Stage II

Given the nature of the study (pilot) and associated small sample size, descriptive statistics will be calculated, but no group comparisons will be completed.

Primary Outcome 2.1 (Comprehension & Recall): The Personal Information and Meaning of Information accuracy scores will be totaled for all participants. Mean, median, and standard deviation will be calculated. Exploratory analyses will evaluate trends in whether specific types of feedback information (e.g., neuroimaging vs. amyloid/tau burden) were better understood than others, and whether group differences exist (i.e., participants vs. co-participants, by race, by cognitive status).

Primary Outcome 2.2 (Psychological Reactions): Mean, median, and standard deviation of total scores on the GDS-15, BAI, and IES will be calculated. Change in total scores on the BAI and GDS-15 will be calculated by comparing Stage II scores with Stage I screening scores. Descriptive statistics will also be calculated for these change scores.

Secondary Outcome 2.3 (Satisfaction): Answers to the qualitative questions will be reviewed individually for suggestions and themes.

SECTION 4: MONITORING

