4.1 Risk Monitoring

4.1.1 Stage I

It is not expected that discussing DAT risk disclosure preferences or needs will cause significant distress or exacerbation of mood symptoms; however, all participants in the Year 1 Needs Assessment will complete a brief measure of mood and anxiety, including the Geriatric Depression Scale – 15 Item version (GDS-15)¹ and the Beck Anxiety Inventory (BAI)² following participation in the semi-structured interview. A study team member will also be present in the room, or available virtually with the participant or co-participant for the entirety of the session to monitor distress. Each of the measures have empirically supported cut-off scores for determining clinically significant depression, anxiety, and event-related distress; individuals who endorse clinically significant depression or anxiety on the GDS-15 or BAI at the end of the session, or who appeared distressed during the session, will undergo a risk assessment and follow-up (see below). The study safety plan to determine need for risk assessment or intervention is included in Appendix A. Of note, for video or phone sessions, at the start of each session, the participant/co-participant will be asked to provide a call-back number in case he/she is disconnected from the technology, as well as current location; this information will not be stored in the participant's/co-participant's file, but will be used as a reference in case of emergency or safety issue.

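### The 'baseline' anxiety and depression predictors in the Stage I 1.3 model are end-of-session scores taken after the outcome, so their coefficients cannot be read as baseline effects and may be biased

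*Combined protocol and SAP*

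**What the plan says.** Section 3.4.2.1 plans mixed linear models for level of interest in disclosure. The fixed effects come in four sets: "participant factors [demographics, baseline anxiety and depression, DAT knowledge" as the first, then ADI perceived threat, perceived benefits and perceived barriers. A random effect covers the dyad.

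Section 3.3.1 (Stage I) sets the order of the session. Once eligible, people "will continue the session to complete questionnaires and a semi-structured interview". The questionnaires include the interest ratings, which are the 1.3 outcome, and the ADI. The BAI and GDS-15 come last: "Geriatric Depression Scale – 15 Item after these procedures, in order to monitor anxiety and mood". Section 4.1.1 agrees. It places the two scales "following participation in the semi-structured interview" and uses them to pick out "individuals who endorse clinically significant depression or anxiety on the GDS-15 or BAI at the end of the session" for risk assessment.

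No earlier Stage I mood measure is described. Section 3.3.2 gives the two scales before the disclosure session, but only in Stage II, which is planned for 10 dyads. Section 3.4.2.2 uses a third label: Stage II change is found by "comparing Stage II scores with Stage I screening scores".

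**The concern.** A predictor called baseline should be recorded before the outcome it is meant to explain. Here the interest rating and the ADI are completed first, and the mood scales follow a session of 90 to 120 minutes about dementia threat and disclosure. If that session, or the act of stating interest, shifts the mood scores, the scores are partly a consequence of the outcome and of the other predictors. The model can then show an association between anxiety and interest that runs the wrong way, and it can over-adjust the threat, benefits and barriers coefficients.

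The protocol accepts that order matters within the session. Section 3.3.1 counter-balances questionnaires and interview questions against priming. The mood scales have a fixed place at the end, so counter-balancing does not protect them.

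At stake is the predictor part of a primary Stage I question. Whatever the size of any bias, reporting these coefficients as baseline effects would misstate the order of measurement.

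**Working it through.** **Timing.** The documents give no effect size or power figure for 1.3, so there is no figure to reproduce. The check is one of order:

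| Item | Place in the Stage I session | Source |
|---|---|---|
| Interest rating (1.3 outcome) | Questionnaires | 3.3.1 |
| ADI (threat, benefits, barriers) | Questionnaires | 3.3.1, 3.4.2.1 |
| Interview | With the questionnaires, order counter-balanced | 3.3.1 |
| BAI and GDS-15 | After all of these | 3.3.1, 4.1.1 |

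The plan does not say that mood scores will be imported from the parent studies. An import could not be relied on for the whole model either: Section 3.1.1 does not require co-participants to be enrolled in those studies, and the model includes both dyad members.

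**What the timing could do.** Every input here is assumed. Let pre-session anxiety A0 and threat T have SD 1 and correlation 0.3. Let interest be Y = 0.3T + e, with residual variance 1 and no true anxiety effect. Let the end-of-session score be A1 = A0 + gT + hY + u, where u has SD s. The dyad effect is ignored. Regressing Y on T and A1 gives, in large samples:

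- anxiety slope = h / (0.91 + h² + s²), where 0.91 = 1 − 0.3²
- threat slope = 0.30 − anxiety slope × (0.3 + g + 0.3h)

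| g = h | s | Anxiety slope (true 0) | Threat slope (true 0.30) |
|---|---|---|---|
| 0 | any | 0 | 0.30 |
| 0.1 | 0.3 | 0.1/1.01 = 0.099 | 0.30 − 0.099 × 0.43 = 0.257 |
| 0.1 | 1.0 | 0.1/1.92 = 0.052 | 0.30 − 0.052 × 0.43 = 0.278 |
| 0.2 | 0.3 | 0.2/1.04 = 0.192 | 0.30 − 0.192 × 0.56 = 0.192 |
| 0.2 | 0.5 | 0.2/1.20 = 0.167 | 0.30 − 0.167 × 0.56 = 0.207 |
| 0.2 | 1.0 | 0.2/1.95 = 0.103 | 0.30 − 0.103 × 0.56 = 0.243 |

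The scaling matters slightly. If interest is given total variance 1 (residual variance 0.91), the 0.192 becomes 0.202.

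**What drives the result.**

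- With h = 0 the anxiety slope is 0 and the threat slope stays at 0.30 for any g. When anxiety has no true effect, bias needs carry-over from the interest response.
- The direction is not fixed. With total variance 1, g = 0, h = −0.2 and s = 0.3, the threat slope is 0.342 and the anxiety slope −0.176.
- If anxiety has a true effect of 0.20 (s = 0.3), a threat-driven shift alone is enough. With h = 0, threat slope = 0.36 − 0.182 × (0.3 + g), which is 0.287 at g = 0.1 and 0.251 at g = 0.3. The anxiety slope is 0.182.

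**Precision, for scale.** With 100 to 120 respondents, and threat and residual SD 1, the standard error of the threat slope is roughly 1/√100 = 0.10 to 1/√120 = 0.09. The shift at 0.1 (0.30 − 0.257 = 0.043) is under half a standard error. At 0.2 (0.30 − 0.192 = 0.108) it is about one.

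**Leaving mood out.** With a true anxiety effect of 0.20 and correlation 0.3, omission gives a threat slope of 0.30 + 0.20 × 0.3 = 0.36. This error of 0.06 is similar in size to those above.

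**The case against.** The best defence is that the scores may barely move. Section 3.3.2 describes the GDS-15 as covering two weeks and the BAI one week, and Section 4.1.1 expects no significant distress from the Stage I discussion. The monitoring rule rests on clinical cut-offs, which concern level and not change, so one score could reasonably serve both as a cut-off check and as a general mood covariate. This stands as an argument about size. It does not place the score before the outcome.

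A second defence is that baseline means Stage I relative to Stage II. That suits the change scores in Section 3.4.2.2. It does not suit a predictor inside a Stage I model.

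Third, the model is cross-sectional. Because questionnaire order is counter-balanced, the ADI may also follow the interest rating, so moving the mood scales would not make 1.3 causal. This is correct. But the plan does not call the ADI a baseline measure, and its order varies, whereas the mood scales always come last.

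Two stronger readings are tempting. A reader might infer that the threat, benefits and barriers coefficients are certainly or heavily biased. The documents contain nothing on how far the session moves mood, and large distortions appear only under sizeable assumed carry-over from interest to anxiety. A reader might also infer that all of question 1.3 is compromised. Section 2.2 shows that 1.3 also asks whether the racial groups differ in perceived threat, benefits and barriers, and the timing of the mood scales in this model does not touch that comparison.

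**Conclusion.** The point holds as a fault of timing and labelling. The plan names a baseline predictor, and the only Stage I score described follows both the outcome and the other perception measures. The bias is possible but cannot be sized from the documents. It is about nil if the session leaves the scores alone. Under the assumed model with no true anxiety effect, the threat slope of 0.30 becomes about 0.26 to 0.28 for 0.1 SD shifts from both threat and interest, and about 0.19 to 0.24 for 0.2 SD shifts. In those cases the anxiety coefficient moves further than the threat coefficient. These figures rest on the assumed correlation, noise and carry-over. The recall windows make the larger shifts less likely.

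**What to change.** **Remaining Stage I sessions.** Give the GDS-15 and BAI after consent and before the questionnaires and interview. For virtual visits the consent call is already in place: "Prior to other study activities, a study team member will set up a phone call to review the consent paperwork together". In-person visits have no separate call, so the scales would follow consent at the start of the session. Define this score as the baseline mood predictor in 1.3, and leave the end-of-session administration unchanged for monitoring.

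**People already seen.** Label their score end-of-session and do not merge it with pre-session scores as one variable. Everyone will have an end-of-session score, so one specification can be fitted to the whole sample and reported with and without it. Both versions are needed, because omitting mood can itself confound the threat slope. Do not interpret the coefficient of the end-of-session score as a baseline effect on interest. Where both scores exist, fit the model with the pre-session score and report the difference between the two, which would show directly how far the session moves mood.

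**Labels.** Reconcile the term used for the Stage I scores in Section 3.4.2.2 with their actual timing, and state which administration is the reference for Stage II change.

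**Cost.** A few extra minutes per session and short edits to Sections 3.3.1, 3.4.2.1 and 3.4.2.2. Early participants will have no true baseline mood score. Enrolment began in October 2019 and the IRB approval date is January 2022, so the pre-session measure may reach few people. The relabelling and the paired reporting need no new data and apply in any case.
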